# Table 20Estimated Response Rate and 80% Two-sided Confidence Interval Out
of Confidence Interval Out
of Confidence Interval Out
(Cohort B2)

Number (%) of Complete Responses a	(20%)	(25%)	(30%)	(35%)	(40%)	(45%)
C	CCI	CCI	CCI	CCI	CCI	CCI
CCI	CCI	CCI	CCI	CCI	CCI	CCI

a Complete response per Modified Lugano Criteria (Complete Response Rate for Cohort B2).
 b CI obtained from exact binomial distribution.
 Abbreviation: CI: confidence interval.

# 9.3 **Populations for Analyses**

For purposes of analysis, the study populations are defined as provided in Table 21. For the safety and PK analyses, participants will be classified according to the dose level they actually received. For all efficacy analyses, and for baseline and demography, participants will be classified according to the dose they were assigned to (ie, the planned treatment/dose level/dose schedule).

Population/Analysis set	Description	Endpoint/Output
Enrolled	All participants who sign the Informed Consent Form, or whose legally authorized representative a sign the Informed Consent Form.	Disposition
Full / Safety	All participants who received any amount of study intervention	Exposure Safety Baseline and demography PFS OS
Interim safety	All participants who received the first dose at least 6 weeks prior to data cut-off	Safety at interim
DLT-evaluable	Participants enrolled in the dose escalation phase who have received sabestomig and completed the DLT evaluation period (defined as 28 days after the start of study intervention) or who experience any DLT	DLT
Response-evaluable	All dosed participants who had measurable disease at baseline	ORR CRR BOR Duration of response Duration of complete response
Interim response-evaluable	All dosed participants who had measurable disease at baseline and received first dose at least 10 weeks prior to data cut-off	Efficacy at interim
РК	All participants who received at least 1 dose of study intervention with at least 1 reportable concentration	PK concentrations PK parameters
Pharmacodynamics	All participants who received at least 1 dose of study intervention with at least 1 reportable pharmacodynamic measurement	Pharmacodynamic endpoints
Immunogenicity	All participants who received at least 1 dose of study intervention with at least 1 reportable immunogenicity measurement	
Exploratory biomarkers	All participants that participate in the exploratory biomarker research	Biomarker endpoints

#### Table 21Study Populations

Legally authorized representative will be required to sign a statement of informed consent and informed assent from the participant (as appropriate) that meets the requirements of 21 CFR 50, local regulations, ICH guidelines Health Insurance Portability and Accountability Act requirements, where applicable, and the IRB/IEC or study center.

Individual PK concentration and parameter data for any participants not included in the PK analysis set or excluded from the descriptive summary tables, figures, and/or inferential statistical analyses will be included in the listings and flagged with an appropriate footnote.

DoR is reported for the subset of participants with objective response.

DoCR is reported for the subset of participants with complete response.

Abbreviations: BOR: best overall response; CRR: Complete Response Rate; DLT: dose-limiting toxicity; DoR: Duration of Response; DoCR: Duration of Complete Response; ORR: Objective Response Rate; OS: Overall Survival; PFS: Progression-free Survival; PK: pharmacokinetic(s).

# 9.4 Statistical Analyses

The SAP will include a more technical and detailed description of the statistical analyses described in this section. This section is a summary of the planned statistical analyses of the most important endpoints including primary and key secondary endpoints. Any deviations from this plan will be reported in the CSR.

### 9.4.1 General Considerations

Analysis will be performed by AstraZeneca or its representatives, including CROs. A comprehensive SAP will be developed and will describe the patient populations to be included in the analyses, the analyses including any subgroup analyses or sensitivity analyses, and the procedures to account for missing, unused, and spurious data.

Data will be presented by dose level in Part A and cohorts in Part B; no direct statistical comparisons will be made between any 2 dose levels or cohorts. For Cohort B1, participants treated at the RP2D in Part A will be included.

Continuous variables will be summarized by the number of observations, mean, standard deviation, median, minimum, and maximum. Geometric mean and coefficient of variation may be presented as applicable. Categorical variables will be summarized by frequency counts and percentages for each category. Unless otherwise stated, percentages will be calculated based on the population total, by dose level or cohort and by time point as appropriate. Time to event variables will be presented using the Kaplan-Meier methodology including median time calculated from the Kaplan-Meier curves.

An interim analysis will be performed as detailed in Section 9.5.

The primary analysis for Part B will be conducted at least 3 months after the final enrolled participant has received their first dose of sabestomig.

A final analysis may be performed 6 months after the last participant begins treatment or when AstraZeneca stops the study, whichever occurs first.

SAS® version 9.4 (as a minimum) will be used for analyses presented in CSR.

Baseline will be considered the last non-missing value obtained prior to the first dose of study intervention. Any information taken after first dose of study intervention will be regarded as post-baseline information. Detailed rules for deriving baseline values are described in the SAP.

Unless stated otherwise, two-sided cIs will be produced at 95%.

As appropriate, time windows will be defined for data summaries presented by visit. Time windows are described in the SAP.

Depending on the extent of any impact, summaries of data relating to participants diagnosed with COVID-19, and impact of COVID-19 on study conduct (in particular, missed visits, delayed or discontinued study intervention, and other protocol deviations) may be generated. Further details will be provided in the SAP.

# 9.4.2 Efficacy Analyses

The efficacy endpoints of ORR, CRR, DoR and DoCR will be summarized on the response-evaluable analysis set. The efficacy endpoints of, PFS, and OS will be summarized on the full analysis set. Additional subgroup analysis of efficacy may be performed as specified in the SAP.

### 9.4.2.1 Primary Endpoint(s) Objective Response Rate

The ORR is defined as the percentage of participants with a CR or PR, with the denominator defined as the number of participants in the response-evaluable analysis set.

Data obtained until progression, or last evaluable assessment in the absence of progression, will be included in the assessment of ORR, regardless of whether the participant withdraws from therapy. Participants who discontinue treatment without a response, receive subsequent anti-lymphoma therapy and then respond will not be included as responders in the ORR.

The ORR will include data of all scans, regardless of whether it was scheduled or not.

The ORR will be presented by the number and percentage of participants with a response (CR/PR) including 95% cIs based on exact binomial proportions.

Best overall response will also be summarized by n (%) for each category, with no formal statistical analysis presented.

The ORR as assessed by BICR based on Modified Lugano criteria for lymphoma is the primary efficacy endpoint in Cohort B1 in Dose Expansion. The ORR is a secondary endpoint for Part A Dose Escalation assessed by Investigator based on Modified Lugano criteria and RECIL criteria.

#### **Complete Response Rate**

The CRR is defined as the percentage of participants with a CR, with the denominator defined as the number of participants in the response-evaluable analysis set.

Data obtained until progression, or last evaluable assessment in the absence of progression, will be included in the assessment of CRR, regardless of whether the participant withdraws from therapy. Participants who discontinue treatment without a response, receive subsequent anti-lymphoma therapy and then respond will not be included as responders in the CRR.

The CRR will include data of all scans, regardless of whether it was scheduled or not.

The CRR will be presented by the number and percentage of participants with CR including 95% cIs based on exact binomial proportions.

The CRR as assessed by BICR based on Modified Lugano criteria for lymphoma is the primary efficacy endpoint in Cohort B2 in Dose Expansion. The CRR is a secondary endpoint for Part A Dose Escalation assessed by Investigator based on Modified Lugano criteria and RECIL criteria.

# 9.4.2.2 Secondary Endpoint(s) Duration of Response

The DoR is defined as the time from the date of first documented response, assessed by Investigator for Part A and by BICR for Cohorts B1 and B2, using the Modified Lugano criteria, until the date of documented progression or death due to any cause (in the absence of disease progression). The end of response should coincide with date of progression or death from any cause used for the PFS endpoint. The time of the initial response will be defined as the latest of the dates contributing towards the first visit that was CR or PR.

The analysis will include all participants in the response-evaluable analysis set who had a response, regardless of whether the participant withdraws from therapy.

If a participant does not progress following a response, then the DoR will use the PFS censoring time.

Kaplan-Meier plots of DoR will be presented if data permitted. Median DoR, including 95% CIs, will also be presented, calculated from the Kaplan-Meier curve. In addition, the number of participants still responding at 3, 6, and 12 months after initial response will also be presented. Swimmer plots that clearly show the profile of each participant who responds will also be produced.

#### **Duration of Complete Response**

The DoCR is defined as the time from first documented CR, assessed by the Investigator for Part A and by BICR for Cohorts B1 and B2, using Modified Lugano criteria, until the date of documented relapse/progression or death due to any cause (in the absence of disease progression).

The analysis will include all participants in the response-evaluable analysis set who had a response, regardless of whether the participant withdraws from therapy.

If a participant does not progress following a response of CR, then the DoCR will use the PFS censoring time.

Kaplan-Meier plots of DoCR will be presented if data permitted. Median DoCR, including 95% CIs, will also be presented, calculated from the Kaplan-Meier curve. In addition, the number of participants still responding at 3, 6, and 12 months after initial response will also be presented. Swimmer plots that clearly show the profile of each participant who responds will also be produced.

#### **Progression-free Survival**

PFS is defined as the time from first dose until the earlier of the date of first documented disease progression, per Lugano classification as assessed by the Investigator for Part A (by BICR for Cohorts B1 and B2), or death (by any cause in the absence of disease progression or subsequent anticancer treatment). Participants who have not progressed or died at the time of analysis, or have unknown status, will be censored at the time of the latest date of assessment from their last evaluable assessment. Additional information and supportive/sensitivity analyses will be provided in the SAP.

The PFS time will always be derived, based on scan/assessment dates, not visit dates.

Disease assessments/scans contributing toward a particular visit may be performed on different dates. The following rules will be applied:

- Date of progression will be determined, based on the earliest of the dates of the component that triggered the progression.
- When censoring a participant for PFS, the participant will be censored at the latest of the dates contributing to a particular overall visit assessment.

Kaplan-Meier plots of PFS will be presented. Summaries of the number and percentage of participants experiencing a PFS event, and type of event (progression or death) will be provided along with the median PFS, its 95% CI and the proportion of participants who were progression free at 3, 6, 12, 18, and 24 months.

The treatment status at progression of participants at the time of the analysis will be summarized. This will include the number and percentage of participants who were on treatment at the time progression, the number and percentage of participants who discontinued study intervention prior to progression, the number and percentage of participants who have not progressed and were on treatment or discontinued treatment. This will also provide a distribution of number days prior to progression for participants who have discontinued treatment.

#### **Overall Survival**

The OS is defined as the time from the start of treatment until death due to any cause regardless of whether participant withdraws from treatment or receives another antilymphoma therapy. Any participant not known to have died at the time of analysis will be censored based on the last recorded date on which the participant was known to be alive.

Note: Survival follow-up phone calls will be made in the week following the date of DCO for the analysis, if participants are confirmed to be alive or if the death date is after the DCO date the participants will be censored at the date of DCO.

The OS data will be presented similarly to the presentation described for PFS.

#### 9.4.3 Safety Analyses

Safety and tolerability will be assessed in terms of DLTs, AEs/SAEs, imAEs, vital signs, clinical chemistry/hematology parameters, and clinically significant abnormalities in ECGs. These variables will be collected for all participants where applicable. All safety analyses will be performed on the safety analysis set. Additional subgroup analysis of safety may be performed, as specified in the SAP.

#### 9.4.3.1 Maximum Tolerated Dose Evaluation

The MTD evaluation will be based on the DLT-evaluable population. After each escalation stage is completed, final DLT rates at each dose level will be estimated by isotonic regression (Ji et al, 2010). The weighted least squares regression model will assume monotonic non-decreasing DLT rates with increasing dose, and use the empirical (observed) DLT rates at each dose level as responses and dose level sample sizes as weights, along with the pool adjacent violators algorithm to estimate the DLT rate at each dose level using available software such as EAST® and R. Given the DLT estimates for each dose level, the MTD will be selected from all tried dose levels that have not been previously declared to be unsafe (Probability [DLT > 30% data]  $\geq$  80%) with a DU decision according to the mTPI-2 decision table. With this constraint, the MTD will be determined as the dose level with the DLT estimate closest to the target toxicity level of 30%.

In the case of dose levels with estimated toxicity of equal distance (tied dose levels) from the target toxicity of 30%, the following approach will be used (Ji et al, 2010): among all tied dose levels, the highest dose level with target toxicity  $\leq$  30% will be selected, unless all tied dose levels have estimated toxicity > 30%, in which case the lowest dose level will be selected.

The number and percentage of participants with a DLT will also be presented by dose level.

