# 4.3.3 Clinical References for PD-1 and TIM-3 Targeting Agents to Support Starting Dose Selection for Sabestomig

Several PD-1 targeting agents have been approved for a broad range of both solid tumor and hematological indications and are established as SoC treatments. Pembrolizumab (KEYTRUDA®) and nivolumab (OPDIVO®) have been the first PD-1 targeting agents to be approved for the treatment of adult patients with cHL that has relapsed or progressed after

SoC treatment including autologous hematopoietic stem cell transplantation and brentuximab vedotin. Both PD-1 targeting agents have a well characterized benefit-risk profile (USPI OPDIVO® and USPI KEYTRUDA®) across solid and hematologic indications.

Publicly available data regarding AEs of TIM-3 in combination with PD-1 targeting agents (Curigliano et al, 2019, Weiss et al, 2017, Lakhani et al, 2020) indicate a safety profile consistent with what has been shown for other PD-1 checkpoint targeting inhibitors (Wang et al, 2019). Immune-mediated AEs associated with these agents are monitorable and manageable based on well-established TMGs (Brahmer et al, 2018, Puzanov et al, 2017).

Sym021 is a humanized IgG1 mAB targeting PD-1 and Sym023 is a recombinant, fully human antibody that binds TIM-3 (Lakhani et al, 2020). A FIH Phase 1 dose escalation study combining Sym021 with Sym022 (anti-LAG) or Sym021 with Sym023 (anti-TIM-3) in advanced or metastatic solid tumor malignancies or lymphomas is ongoing (NCT03311412). The dose escalation studies of Sym021, Sym022, and Sym023 as singe agents has been completed. The MTD was not reached for any single agent. The Sym021 dose was fixed at 3 mg/kg based on PK/pharmacodynamic analysis for subsequent combination with Sym022 or Sym023. The MTD was not reached for any combination. Part 2 Arm B combining Sym021 RP2D with Sym023 enrolled 17 patients and was well tolerated with AE profiles typical of IC inhibitors. The most commonly observed Grade 3 or Grade 4 treatment-related adverse events included 5 events: ALT increase (5.9%), lymphopenia/lymphocytes decreased (5.9%), fatigue (5.9%), cough (5.9%) and rash (5.9%). Objective responses in the Part 2 Arm B combination of Sym021+Sym023 included 2 PRs. Evaluation of antitumor activity of Sym021+023 doublets in select tumor types post-PD-1/PD-L1 treatment are planned.

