#### 6.6.1.2 Modified Toxicity Probability Interval

A minimum of and a maximum of participants will be enrolled at a given dose level for Part A. Dose escalation to the next dose level will be conducted using the mTPI-2 algorithm with a target DLT rate of 30% and an equivalence interval (25%, 33%). A minimum of participants must complete the DLT evaluation period before making an escalation decision. Dose escalation will consist of 4 planned dose levels of sabestomig. Intermediate dose levels may be explored if warranted by emerging safety, PK, pharmacodynamic, biomarker, and efficacy data. Dose escalation and de-escalation recommendations will follow the mTPI-2 algorithm schema below:

- 1 A minimum of evaluable participants are required in each dose level unless unacceptable toxicity is encountered in the first participants prior to enrollment of the third participant, which would require dose de-escalation per the mTPI-2 algorithm. For a dose level that has fewer than participants who are DLT-evaluable, participants will be replaced.
- 2 If a de-escalation decision is made, choice of de-escalation to the previous dose level will be at the discretion of the SRC. In the eventuality that a decision is made to de-escalate back to a dose escalation level that was previously deemed safe, and into which mini expansion cohort participants have since been enrolled at that dose level, these mini-expansion cohort participants may be included in further dose escalation decisions.
- 3 If a stay ("S") decision is made, additional participants will be enrolled up to a maximum of participants for a given dose level.
- 4 Administration of the first dose of sabestomig will be staggered by a minimum of 24 hours between the first and second participants in each dose escalation cohort. Intraparticipant dose escalation will not be allowed during the mTPI-2 part of dose escalation.
- 5 At the discretion of AstraZeneca, dose escalation may be stopped before an MTD is reached.
- 6 The MTD will be determined by isotonic regression analysis applied to DLT rates observed during dose escalation using the mTPI-2 method (Ji et al, 2010).

Participants enrolled into ATD dose escalation cohorts may be considered evaluable for dose escalation decision-making purposes using mTPI-2 algorithm if the dose under investigation is identical to one previously assessed by ATD dose escalation.

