#### Description of the Modified Toxicity Probability Interval-2 Algorithm

The mTPI-2 algorithm employs a simple beta-binomial Bayesian model. The prior distribution for all dose levels is Beta(1,1). The posterior distribution for all dose levels is Beta(1+a, 1+b), where a and b are the number of participants with and without a DLT at the current dose level, respectively. The posterior density of the toxicity probability is divided into multiple intervals with equal length. These intervals are categorized as underdosing, proper dosing, and overdosing in terms of toxicity. The underdosing interval corresponds to a dose escalation, overdosing corresponds to a dose de-escalation, and proper dosing corresponds to staying at the current dose. Given an interval and a probability distribution, the unit probability mass of that interval is defined as the probability of the interval divided by the length of the interval. The design for the dose escalation phase of the study uses a target DLT rate of 30% and an equivalence interval (25%, 33%) for dose escalation/de-escalation decisions as well as MTD determination. A dose level will be considered unsafe, with no additional participants enrolled at that dose level, if it has an estimated 80% or more probability of exceeding the target DLT rate of 30% (ie, Probability  $[DLT > 30\% \text{ data}] \ge 80\%$ ) with at least participants treated and evaluated at that dose level. In Table 15, dose escalation/de-escalation decision rules are computed based on the above information.

Number		Number of Evaluable Participants Treated at Current Dose Level										
of DLTs	1	2	3	4	5	6	7	8	9	10	11	12 °
0	S a	S a	Е	Е	Е	Е	Е	Е	Е	Е	Е	Е
1	S b	S b	S e	S	Е	Е	Е	Е	Е	Е	Е	Е
2		DU d	DU	DU	D	D	S	S	Е	Е	Е	Е
3			DU	DU	DU	DU	DU	D	D	S	S	Е
4				DU	DU	DU	DU	DU	DU	D	D	D
5					DU							

 Table 15
 Modified Toxicity Probability Interval-2 Algorithm

a Changed from "E" to "S" as a minimum of evaluable participants are needed to make a dose escalation decision.

b Changed from "D" to "S" as a minimum of evaluable participants are needed to make a dose escalation decision.

c The "S" cells in original modified toxicity probability interval-2 algorithm are modified to either E or D according to whether the observed DLT rate is < or  $\ge$  the target toxicity of 30%, respectively.

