#### 6.6.4 Definition of Maximum Tolerated Dose

The MTD will be selected from all tried dose levels that have not been previously declared to be unsafe with a DU decision according to the mTPI-2 algorithm. With this constraint, the MTD will be determined as the dose level with the DLT estimate closest to the target toxicity level of 30%.

In the case of dose levels with estimated toxicity of equal distance (tied dose levels) from the target toxicity of 30%, the following approach will be used (Ji et al, 2010): among all tied dose levels the highest dose level with target toxicity  $\leq$  30% will be selected, unless all tied dose levels have estimated toxicity  $\geq$  30%, in which case the lowest dose level will be selected.

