4.5.10 Other Safety Assessments

4.5.10.1 Definitions and Derivations

Maximum Tolerated Dose (MTD) Evaluation

See Section 9.4.3.1 of the CSP for the definition of a DLT.

After the escalation phase is completed, DLT rates at each dose level will be estimated by isotonic regression (Ji et al, 2010). The weighted least squares regression model conditional on monotonic non-decreasing DLT rates with increasing dose and use the empirical (observed) DLT rates at each dose level as responses and sample sizes at each dose level as weights, along with the pool adjacent violators algorithm (PAVA) to estimate the DLT rate at each dose level using available software (eg, Cytel EAST or the function pava() from the

R package 'ISO'). Given the DLT estimates for each dose level, the MTD will be selected from all tried dose levels that have not been previously declared to be unsafe with a "deescalate to the previous lower dose and the current dose will be never used again due to unacceptable toxicity" (DU) decision according to the mTPI-2 decision table. With this constraint, the MTD is determined as the dose level with the DLT estimate closest to the target toxicity level of "%."

In the case of dose levels with estimated toxicity of equal distance (tied dose levels) from the target toxicity of "%, the following approach is used (Ji et al, 2010) among all tied dose levels the highest dose level with target toxicity "CC" will be selected, unless all tied dose levels have estimated toxicity "CC", in which case the lowest dose level will be selected.

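### The MTD rule has no 'MTD not reached' outcome: if no DLTs occur, it labels the highest dose tried as the MTD, against the plan's own escalation section

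*Protocol*

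**What the plan says.** Protocol 9.4.3.1 states that "final DLT rates at each dose level will be estimated by isotonic regression". Among tried doses without a DU decision, "the MTD will be determined as the dose level with the DLT estimate closest to the target toxicity level of 30" per cent. SAP 4.5.10.1 repeats that "the MTD is determined as the dose level with the DLT estimate closest to the" target (the figure is blacked out there), as does SAP 3.3.7.1. Protocol 6.6.4 gives the same definition.

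Ties go to the highest tied dose at or below 30%. There is one exception, "in which case the lowest dose level will be selected". Section 9.4.3.1 applies it when all tied estimates are above 30%, and 6.6.4 when all are at or above 30%. The SAP's inequalities are blacked out.

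Two other statements in Protocol 6.6.1.2 bear on this. Item 5 says "dose escalation may be stopped before an MTD is reached", at the sponsor's discretion. The description of the mTPI-2 algorithm says that the 30% target and the 25% to 33% equivalence interval serve MTD determination as well as escalation decisions. SAP 3.3.7.1 carries the same sentence with the numbers blacked out. SAP section 2 lists no change to the protocol's planned analyses.

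**The concern.** A dose called the MTD is understood to carry a DLT rate near the target, here 30%. The selection rule measures only which dose is nearest, not whether it is near. With few or no DLTs, the nearest dose can have an estimate of 0% and still receive the label.

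The plan acknowledges that escalation may end without an MTD, and it reports that outcome for related agents. For the antibodies described in Protocol 4.3.3, "The MTD was not reached for any single agent", and the same is said of their combinations and of another anti-TIM-3 antibody given alone. An analyst who follows 9.4.3.1 or SAP 4.5.10.1 literally could not report that result here. Establishing the MTD, or the optimal biological dose (OBD), is a primary objective of Part A, so the label belongs to a primary deliverable.

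**Working it through.** **Inputs.** Target 30%, interval 25% to 33%, Beta(1,1) prior, DU if P(DLT rate > 30%) is at least 80% (Protocol 6.6.1.2). Isotonic regression weighted by sample size (9.4.3.1). Eight planned doses, four with 1 participant and four with 3 to 12, at most 52 in Part A (SAP 3.3.7 and 3.3.7.2).

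**1. The plan's own figures.** Taking the largest unit probability mass over intervals of width 0.08 under Beta(1+a, 1+b), with the DU rule, gives 48 of the 54 legible cells of Table 15. The other six (0/1, 0/2, 1/1, 1/2, 1/3, 3/12) are those its footnotes change by hand. Part A size: 4×1 + 4×12 = 52, as stated. The algorithm is therefore read correctly.

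**2. The MTD step on example data.**

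| Data | Isotonic estimates | Dose named |
|---|---|---|
| 0 DLTs at all eight doses (3 or 12 per mTPI-2 dose) | all 0%, all 30 points from target | 2000 mg |
| 0 DLTs, optional 2000 mg cohort not opened | all 0% | 1500 mg |
| 1/12 at 750 mg, 0/3 at 225, 1500 and 2000 mg | 1/(12+3+3) = 5.6% at the top three doses | 2000 mg |
| Only dose tried has 3/3 (DU) | 100% | none |

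The last row is the only kind of case in which no dose is named: every tried dose is DU.

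**3. What a 0% estimate supports.** The exact 95% upper limit for 0/n is 1 − 0.025^(1/n): 70.8% for 0/3 and 26.5% for 0/12. With 0/12 the interval excludes the 30% target, yet the rule would still call that dose the MTD if it were the highest tried.

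**4. How often, under assumed rates.** The documents give no DLT rate for this drug. As a range only, Protocol 2.3.1 cites Grade 3 to 4 AEs in about 4% to 11% of participants on anti-TIM-3 agents; these are not DLT rates. With a flat rate p, P(no DLT) = (1 − p)^N:

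- N = 16 (4×1 + 4×3): 0.96^16 = 52%; 0.89^16 = 16%.
- N = 52: 0.96^52 = 12%; 0.89^52 = 0.2%.

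A wider count asks how often the named dose has an estimate below 25%, the plan's lower interval limit. In 20,000 simulated trials per setting, with four mTPI-2 doses and equal numbers per dose:

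| Assumed flat rate | 3 per dose | 6 per dose | 12 per dose |
|---|---|---|---|
| 5% | 85% | 96% | 98% |
| 10% | 70% | 84% | 88% |

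At 5%, the chance of no DLT at these four doses is 0.95^12 = 54%, 0.95^24 = 29% and 0.95^48 = 9%. Equal numbers are not this design. Running Table 15 sequentially in assumed cohorts of 3 (the added-cohort size is redacted) gave 98% at a 4% rate and 85% at 11%. Another coding gave 93% at 5% and 79% at 10%. These are orders of magnitude, not predictions.

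**5. Tie wording.**

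| Tied data at two doses | Estimates | 9.4.3.1 names | 6.6.4 names |
|---|---|---|---|
| 3/10 and 3/10 | 30%, 30% | higher | lower |
| 2/6 then 1/4 | pooled 3/10 = 30% | higher | lower |
| 4/12 and 4/12 | 33.3%, 33.3% | lower | lower |

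Over all two-dose outcomes with 3 to 12 per dose (85 × 85 = 7225), the wordings differ in 9, all with both estimates at exactly 30%.

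**The case against.** The best defence is that the plan read as a whole already recognises the outcome. Section 6.6.1.2 says escalation may stop without an MTD and links the 25% to 33% interval to MTD determination. The objective is the MTD or the OBD, so Part A does not need an MTD. Section 9.4.3.1 also requires DLT counts and percentages by dose, so 0/n would appear beside any named dose. All of this stands and limits the harm. It does not supply the missing branch: the sections that define the analysis neither apply the interval nor say how to report an unreached MTD.

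A reader might infer four stronger things that the documents do not support.

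- That the rule always names a dose. It names none when every tried dose is DU.
- That a false MTD is the likely result. That rests on other agents and assumed rates.
- That the recommended Phase 2 dose would be wrong. Protocol 4.2.1 bases it on the OBD and 6.6.5 on the totality of the escalation data.
- That the tie clauses contradict each other within 9.4.3.1. They cover mutually exclusive cases; the mismatch is only between that section and 6.6.4.

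**Conclusion.** The point holds as a gap and an internal inconsistency in how the MTD is reported. Unless every tried dose is DU, the rule names a dose however far its estimate lies below 30%, and with no DLTs that is the highest dose tried. This follows from the text and needs no assumption. The frequencies do need one: a flat DLT rate, plus fixed or assumed cohort sizes. At low assumed rates the situation is common; the documents cannot say whether it is likely for this drug.

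The effect is on the label attached to a primary deliverable, not on escalation decisions or the stated basis of the recommended Phase 2 dose. It should be corrected, but it does not threaten the trial. The tie mismatch is a small wording conflict with consequences only at estimates of exactly 30%.

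**What to change.** Reconcile Protocol 6.6.1.2 (item 5 and the algorithm description), 6.6.4 and 9.4.3.1 with SAP 3.3.7.1 and 4.5.10.1, so that the analysis can return 'MTD not reached'. In that case, report the highest dose administered with its DLT rate and exact confidence interval. State how the plan's own equivalence interval enters MTD determination, since 6.6.1.2 says that it does and the selection rule does not show it. Use one tie wording in 6.6.4 and 9.4.3.1, and check the SAP against it; which wording is for the sponsor to decide. Label any simulated frequencies quoted in support as resting on assumed DLT rates.

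The cost is a few sentences in the two documents. No escalation decision, dose or sample size changes.
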